4.2. Scientific Rationale for Study Design

The Phase 3 study described in this protocol will provide 20vPnC safety and immunogenicity data of 20vPnC in adults ≥ 18 years of age in India.

4.2.1. Choice of Contraception/Barrier Requirements

Human reproductive safety data are not available for 20vPnC, but there is no suspicion of human teratogenicity based on the intended pharmacology of the compound. Therefore, the use of a highly effective method of contraception is required (see [Section 10.3](#)).

4.3. Justification for Dose

The 20vPnC candidate is modeled after 7vPnC and 13vPnC, and contains capsular polysaccharides from pneumococcal serotypes 1, 3, 4, 5, 6A, 6B, 7F, 8, 9V, 10A, 11A, 12F, 14, 15B, 18C, 19A, 19F, 22F, 23F, and 33F individually conjugated to CRM₁₉₇. The vaccine formulation contains 2.2 μ g of each saccharide, except for 4.4 μ g of 6B, per 0.5-mL dose. In adults, administration of 1 dose of pneumococcal conjugate vaccine induces immune responses.

For this product, the term “dose” refers to an injection of a vaccine.

4.4. End of Study Definition

The end of the study is defined as the date of the last visit of the last participant in the study.

5. STUDY POPULATION

This study can fulfill its objectives only if appropriate participants are enrolled. The following eligibility criteria are designed to select participants for whom participation in the study is considered appropriate. All relevant medical and nonmedical conditions should be taken into consideration when deciding whether a particular participant is suitable for this protocol.

Prospective approval of protocol deviations to recruitment and enrollment criteria, also known as protocol waivers or exemptions, is not permitted.

5.1. Inclusion Criteria

Participants are eligible to be included in the study only if all of the following criteria apply:

Age and Sex:

1. Male or female adults \geq 18 years of age, at Visit 1.
 - Refer to [Section 10.3](#) for reproductive criteria for male ([Section 10.3.1](#)) and female ([Section 10.3.2](#)) participants.

Type of Participant and Disease Characteristics:

2. Participants who are willing and able to comply with all scheduled visits, receipt of study intervention, lifestyle considerations, and other study procedures.
3. Female participant of childbearing potential or male participant who is able to father children and willing to use a highly effective method of contraception, as outlined in [Section 10.3.4](#), for at least 28 days after the dose of study intervention; or female participant not of childbearing potential (defined in [Section 10.3.3](#)) or male participant not able to father children.
4. Participants who are determined by medical history, physical examination (if required), and clinical judgment of the investigator to be eligible for inclusion in the study.

Note: Participants with preexisting stable disease, defined as disease not requiring significant change in therapy or hospitalization for worsening disease during the 12 weeks before enrollment, can be included.

Informed Consent:

5. Capable of giving signed informed consent as described in [Section 10.1](#), which includes compliance with the requirements and restrictions listed in the ICD and in this protocol.

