5.3. Lifestyle Considerations

5.3.1. Contraception

The investigator or his or her designee, in consultation with the participant, will confirm that the participant has selected an appropriate method of contraception for the individual participant and his or her partner(s) from the permitted list of contraception methods (see [Appendix 3: Contraceptive and Barrier Guidance, Section 10.3.4](#)) and will confirm that the participant has been instructed in its consistent and correct use. At time points indicated in the [SoA](#), the investigator or designee will inform the participant of the need to use highly effective contraception consistently and correctly and document the conversation and the participant's affirmation in the participant's chart (participants need to affirm their consistent and correct use of at least 1 of the selected methods of contraception) considering that their risk for pregnancy may have changed since the last visit.

In addition, the investigator or designee will instruct the participant to call immediately if the selected contraception method is discontinued or if pregnancy is known or suspected in the participant or partner.

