10.3. Appendix 3: Contraceptive and Barrier Guidance

10.3.1. Male Participant Reproductive Inclusion Criteria

Male participants are eligible to participate if they agree to the following requirements during the intervention period and for at least 28 days after the last dose of study intervention, which corresponds to the time needed to eliminate reproductive safety risk of the study intervention(s):

- Refrain from donating sperm.

PLUS either:

- Be abstinent from heterosexual intercourse with a female of childbearing potential as their preferred and usual lifestyle (abstinent on a long-term and persistent basis) and agree to remain abstinent.

OR

- Must agree to use contraception/barrier as detailed below:
 - Agree to use a male condom and should also be advised of the benefit for a female partner to use a highly effective method of contraception as a condom may break or leak when having sexual intercourse with a woman of childbearing potential who is not currently pregnant.
 - In addition to male condom use, a highly effective method of contraception may be considered in WOCBP partners of male participants (refer to the list of highly effective methods below in [Section 10.3.4](#)).

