10.3.2. Female Participant Reproductive Inclusion Criteria

A female participant is eligible to participate if she is not pregnant or breastfeeding, and at least 1 of the following conditions applies:

- Is not a WOCBP (see definitions below in [Section 10.3.3](#)).

OR

- Is a WOCBP and using an acceptable contraceptive method as described below during the intervention period (for a minimum of 28 days after the last dose of study intervention). The investigator should evaluate the effectiveness of the contraceptive method in relationship to the first dose of study intervention.

The investigator is responsible for review of medical history, menstrual history, and recent sexual activity to decrease the risk for inclusion of a woman with an early undetected pregnancy.

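### Do the contraception entry rules for men contradict each other on whether a condom alone is enough?

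*Protocol*

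**What the plan says.** Three places in the Protocol set the standard as a highly effective method.

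- Section 4.2.1: "Therefore, the use of a highly effective method of contraception is required", with a pointer to Section 10.3.
- Section 5.1, criterion 3: "Female participant of childbearing potential or male participant who is able to father children and willing to use a highly effective method of contraception", defined by reference to Section 10.3.4 and lasting at least 28 days after the dose.
- Section 5.3.1: "the investigator or designee will inform the participant of the need to use highly effective contraception consistently and correctly". The same section asks the investigator to check that each person "has selected an appropriate method of contraception for the individual participant and his or her partner(s) from the permitted list of contraception methods", which again is Section 10.3.4.

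Criterion 1 sends sites to Section 10.3.1 for men. Besides refraining from sperm donation, a man there must either be abstinent or meet two condom bullets. The first is "Agree to use a male condom and should also be advised of the benefit for a female partner to use a highly effective method". The second is "In addition to male condom use, a highly effective method of contraception may be considered in WOCBP partners of male participants", followed by the direction to "refer to the list of highly effective methods below in" Section 10.3.4.

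Section 10.3.4 lists 12 numbered methods. Items 10 and 12 involve condoms, and item 11 covers other barrier methods. For women, Section 10.3.2 uses a different adjective: "Is a WOCBP and using an acceptable contraceptive method as described below".

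**The concern.** All inclusion criteria must be met together. If the condom bullets in Section 10.3.1 mean that a condom is not itself a highly effective method, a man who will use only condoms satisfies criterion 1 and fails criterion 3. Two sites in this multicenter study could then decide differently about the same man.

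The surrounding rules make such a split awkward. Section 5 permits no waivers of entry criteria, and Section 5.4 does not allow a screen failure to be rescreened. A wrongly excluded man could not return, and a wrongly included one would be an eligibility deviation. The telehealth check in Section 10.6.1 asks sites to confirm the contraception the protocol requires, so it would inherit any ambiguity.

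**Working it through.** There is no figure to reproduce, so the check is whether any man receives two different answers from the text.

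**Step 1: what does highly effective refer to?** Criterion 3 does not leave the term open; it points to Section 10.3.4. Section 5.3.1 sends the investigator to the same list. Section 10.3.1 uses the term three times: twice for a partner's method added to the condom, and once as the label for the whole of Section 10.3.4. In the text available, that list has no sub-heading dividing its 12 items, and condoms are item 10.

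**Step 2: apply both rules to each kind of man able to father children**, assuming he also refrains from sperm donation.

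| Man's intention | Section 10.3.1 | Criterion 3, literal reading (all of 10.3.4 counts) | Criterion 3, contrast reading (condom does not count) |
|---|---|---|---|
| Abstinent as defined | Met | Met (item 8, on its conditions) | Met (item 8, on its conditions) |
| Condom, and partner uses a listed non-barrier method | Met | Met | Met |
| Condom only | Met | Met | Not met |

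The second row counts the partner's method towards criterion 3, because Section 5.3.1 has the method chosen for the participant and his partners together. Only the last row depends on the reading, and under the literal reading it shows no conflict.

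**Step 3: how many men fall in that row?** The documents give no expected sex split or mix of methods, so no number can be put on it. Criterion 3 turns on willingness, and Section 5.3.1 has the method chosen in consultation with the investigator. A man who uses condoms now is therefore not excluded even under the contrast reading. The group is men who would use nothing else on the list, at a site that adopts that reading.

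**Step 4: does it reach the results?**

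- The safety set (Protocol 9.2, SAP 4) is everyone vaccinated with safety data afterwards. Contraceptive method plays no part in it.
- The evaluable immunogenicity set in SAP 4 asks for eligible participants without other major deviations. A condom-only man judged ineligible after vaccination could be dropped from it. That would cost a participant from a subset of about 50 per cohort. It would not bias the fold rise unless contraceptive choice were related to OPA response, and nothing in the documents suggests that it is.
- The study has one arm and no hypothesis test, so there is no comparison for uneven site decisions to distort.

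**Step 5: is participant safety engaged?** Section 4.2.1 states that the vaccine's pharmacology gives no ground to suspect harm to a fetus. The 28-day period is the same in criterion 3 and in Sections 8.9.1, 10.3.1 and 10.3.2, so the duration is not in dispute.

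**The case for a change.** The strongest opposing argument is that the literal reading leaves Section 10.3.1 incoherent. That section advises a highly effective method in the partner precisely because a condom can fail, which makes little sense if the condom already has that status. Section 10.3.4 also does not treat listing as sufficient for every item: items 5 and 8 are called highly effective only on stated conditions. If the formatted protocol carries a sub-heading that separates the later items by effectiveness, the contrast reading gains support, and Section 10.3.1 would admit a man whom criterion 3 does not.

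Part of this stands. The wording is inconsistent, Sections 4.2.1 and 5.3.1 make no exception for men, and a careful site could hesitate. But the contrast is implied. Nowhere in the text does the Protocol say that a condom falls outside the term, whereas the cross-reference in criterion 3 and the label in Section 10.3.1 are explicit. The sub-heading is conjecture about text not available here; if it exists, the list already shows which methods qualify.

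The variety of adjectives adds little. Acceptable, appropriate and permitted are looser labels, and for women they amount to a mismatch of terms around a single list. The telehealth check refers back to Section 10.3 and creates no separate rule.

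**Conclusion.** The point is a slip in terminology. As written, a man willing to use only condoms and to refrain from sperm donation meets both criterion 3 and Section 10.3.1, so no definite eligibility conflict is shown. A site relying on the implied contrast could decide otherwise. The number of men this would touch is unknown and is confined to one row of the table above.

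No change to the plan follows because none would bring a demonstrable gain. Harmonising the term would alter no stated figure, estimate or interval, would not improve the trial's ability to describe safety and immune response, and addresses no shown risk to participants. Sections 4.2.1, 5.1, 5.3.1, 10.3.1 and 10.3.4 do use the term unevenly. Reconciling them is a matter of wording for the sponsor's clinical team, and this review does not say which standard is right.

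The conclusion is held with moderate confidence. It assumes that Section 10.3.4 is the undivided list it appears to be, and that contraceptive choice is unrelated to reactogenicity or OPA response. If the list is divided, the eligibility conflict for condom-only men becomes real, but the reasoning about the analyses is unchanged.

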5.2. Exclusion Criteria

Participants are excluded from the study if any of the following criteria apply:

Medical Conditions:

1. History of severe adverse reaction associated with a vaccine and/or severe allergic reaction (eg, anaphylaxis) to any component of 20vPnC, or to any other diphtheria toxoid-containing vaccine.
2. History of microbiologically-proven invasive disease caused by *S pneumoniae*.
3. Known or suspected immune deficiency or suppression.
4. Bleeding diathesis or condition associated with prolonged bleeding that would, in the opinion of the investigator, contraindicate intramuscular injection.
5. Congenital, functional, or surgical asplenia.
6. Serious chronic disorder, including metastatic malignancy, severe COPD requiring supplemental oxygen, end-stage renal disease with or without dialysis, cirrhosis of the liver, clinically unstable cardiac disease, or any other disorder that in the investigator's opinion would make the participant inappropriate for entry into the study.
7. Other medical or psychiatric condition including recent (within the past year) or active suicidal ideation/behavior or laboratory abnormality that may increase the risk of study participation or, in the investigator's judgment, make the participant inappropriate for the study.
8. Current febrile illness (body temperature $\geq 100.4^{\circ}\text{F}$ [$\geq 38.0^{\circ}\text{C}$]) or other acute illness within 48 hours before study intervention administration.

Prior/Concomitant Therapy:

9. Previous vaccination with any pneumococcal vaccine, or planned receipt of any pneumococcal vaccine through study participation.

10. Receipt of any inactivated or otherwise nonlive vaccine within 14 days or any live vaccine within 28 days before study intervention administration. The exception is recent vaccination of pandemic COVID-19 vaccine (>14 days prior to study enrollment is preferred).
11. Current treatment with immunosuppressive therapy, including cytotoxic agents or systemic corticosteroids, or planned receipt during the study. Participants should not be enrolled into the study until corticosteroid therapy has been discontinued for at least 28 days before study intervention administration. Inhaled/nebulized, intraarticular, intrabursal, or topical (skin, eyes, or ears) corticosteroids are permitted.
12. Receipt of blood/plasma products or immunoglobulin within the 60 days before study intervention administration, or planned receipt during the study.

Prior/Concurrent Clinical Study Experience:

13. Participation in other studies involving investigational drugs, investigational vaccines (with the exception of vaccines authorized by the DCGI for pandemic use), or investigational devices within 28 days prior to study entry and/or during study participation. Participation in purely observational studies is acceptable.

Diagnostic Assessments:

Not applicable.

Other Exclusions:

14. Investigator site staff or Pfizer employees directly involved in the conduct of the study, site staff otherwise supervised by the investigator, and their respective family members.

5.3. Lifestyle Considerations

5.3.1. Contraception

The investigator or his or her designee, in consultation with the participant, will confirm that the participant has selected an appropriate method of contraception for the individual participant and his or her partner(s) from the permitted list of contraception methods (see [Appendix 3: Contraceptive and Barrier Guidance, Section 10.3.4](#)) and will confirm that the participant has been instructed in its consistent and correct use. At time points indicated in the [SoA](#), the investigator or designee will inform the participant of the need to use highly effective contraception consistently and correctly and document the conversation and the participant's affirmation in the participant's chart (participants need to affirm their consistent and correct use of at least 1 of the selected methods of contraception) considering that their risk for pregnancy may have changed since the last visit.

In addition, the investigator or designee will instruct the participant to call immediately if the selected contraception method is discontinued or if pregnancy is known or suspected in the participant or partner.

5.4. Screen Failures

Screen failures are defined as participants who consent to participate in the clinical study but are not subsequently assigned study intervention. A minimal set of screen failure information is required to ensure transparent reporting of screen failure participants to meet the CONSORT publishing requirements and to respond to queries from regulatory authorities. Minimal information includes demography, screen failure details, eligibility criteria, and any SAE.

Individuals who do not meet the criteria for participation in this study (screen failure) may not be rescreened.

6. STUDY INTERVENTION(S) AND CONCOMITANT THERAPY

Study intervention is defined as any investigational intervention(s), marketed product(s), placebo, medical device(s), or study procedure(s) intended to be administered to a study participant according to the study protocol.

For the purposes of this protocol, study intervention refers to 20vPnC.

6.1. Study Intervention(s) Administered

20vPnC will be provided by the sponsor to the study sites.

20vPnC will be packed and labeled as investigational product in accordance with current guidelines and applicable local and legal regulatory requirements.

20vPnC is a sterile liquid suspension formulation containing saccharides from pneumococcal serotypes 1, 3, 4, 5, 6A, 6B, 7F, 8, 9V, 10A, 11A, 12F, 14, 15B, 18C, 19A, 19F, 22F, 23F, and 33F individually conjugated to CRM₁₉₇. The vaccine is formulated to contain 2.2 µg of each saccharide, except for 4.4 µg of 6B, per 0.5-mL dose. The vaccine contains 5 mM succinate buffer, 150 mM sodium chloride, 0.02% polysorbate 80, and 125 µg aluminum as aluminum phosphate, per 0.5-mL dose.

20vPnC will be supplied to the site as packaged, single-use prefilled syringes.

6.1.1. Administration

20vPnC should be administered intramuscularly by injecting 0.5 mL into the deltoid muscle of the non-dominant arm.

Any concomitant vaccines required by local recommendations and permitted by the protocol may be administered concomitantly with 20vPnC but must be given in a different limb.

Standard vaccination practices must be observed, and vaccine must not be injected into blood vessels. Appropriate medication and other supportive measures for management of an acute hypersensitivity reaction should be available in accordance with local guidelines for standard immunization practices.

Administration of study interventions should be performed by an appropriately qualified, GCP-trained, and vaccine-experienced member of the study staff (eg, physician, nurse, physician's assistant, nurse practitioner, pharmacist, or medical assistant) as allowed by local, state, and institutional guidance.

Study intervention administration details will be recorded on the CRF.

6.1.2. Medical Devices

In this study, medical devices being deployed are the prefilled syringes containing 20vPnC. Instructions for medical device use are provided in the IP manual or in the package insert.

Medical device incidents, including those resulting from malfunctions of the device, must be detected, documented, and reported by the unblinded study personnel throughout the study. Please refer to [Section 8.3.9](#) for details.

6.2. Preparation, Handling, Storage, and Accountability

1. 20vPnC will be shipped to the study site after required regulatory and legal documents have been received by the sponsor. 20vPnC will be shipped at +2°C to +8°C. Upon receipt at the study site, the study intervention should be immediately transferred to a +2°C to +8°C temperature-monitored refrigerator for storage. Study intervention must be stored in a horizontal orientation.
2. The investigator or designee must confirm appropriate temperature conditions have been maintained during transit for all study interventions received and any discrepancies are reported and resolved before use of the study intervention.
3. Only participants enrolled in the study may receive study intervention and only authorized site staff may supply or administer study intervention. All study interventions must be stored in a secure, environmentally controlled, and monitored (manual or automated recording) area in accordance with the labeled storage conditions with access limited to the investigator and authorized site staff. At a minimum, daily minimum and maximum temperatures for all site storage locations must be documented and available upon request. Data for nonworking days must indicate the minimum and maximum temperatures since previously documented for all site storage locations upon return to business.

4. Any excursions from the study intervention label storage conditions should be reported to Pfizer upon discovery along with any actions taken. The site should actively pursue options for returning the study intervention to the storage conditions described in the labeling, as soon as possible. Once an excursion is identified, the study intervention must be quarantined and not used until Pfizer provides permission to use the study intervention. Specific details regarding the definition of an excursion and information the site should report for each excursion will be provided to the site in the IP manual or other specified location.
5. Any storage conditions stated in the SRSD will be superseded by the storage conditions stated on the label.
6. Study interventions should be stored in their original containers.
7. The investigator, institution, or the head of the medical institution (where applicable) is responsible for study intervention accountability, reconciliation, and record maintenance (ie, receipt, reconciliation, and final disposition records), such as the IPAL or sponsor-approved equivalent. All study interventions will be accounted for using a study intervention accountability form/record.
8. Further guidance and information for the final disposition of unused study interventions are provided in the IP manual. All destruction must be adequately documented. If destruction is authorized to take place at the investigator site, the investigator must ensure that the materials are destroyed in compliance with applicable environmental regulations, institutional policy, and any special instructions provided by Pfizer.

Upon identification of a product complaint, notify the sponsor within 1 business day of discovery as described in the IP manual.

